Colonoscopy quality report card & reporting infrastructure: The VA-EQuIP quality reporting infrastructure includes 2 separate CDW databases with an extract, transform, loading (ETL) framework and secure SharePoint Site to visually present quarterly colonoscopy quality metrics (**Figure 2**). VA-EQuIP has been pilot tested and undergone iterative usability testing with the Gastroenterology Field Advisory Committee.

Data measures: CDW structured data include patient demographics and endoscopist name and specialty (e.g. gastroenterology, surgery). Variables derived from natural language processing of colonoscopy procedure and pathology notes include extent of exam, screening indication, and adenoma detection.

Outcome measures: The primary outcomes are overall and screening ADR for endoscopists after implementation of the quality report cards, [with an average follow up of 19.5 months (range 12-27 months).] Overall ADR is defined as the percentage of patients undergoing colonoscopy for any indication with one or more adenomas detected. Screening ADR is defined as the percentage of patients ≥ 50 years undergoing screening colonoscopy who have one or more adenomas detected. We will assess secondary outcomes measures, including cecal intubation rate and bowel preparation quality. Cecal intubation is defined as passage of the colonoscopy tip to a point proximal to the ileocecal valve so that the entire cecum is visible. The cecal intubation rate is the proportion of colonoscopies with cecal intubation documented in the procedure note. Bowel preparation quality is determined by the endoscopist for bowel cleanliness allowing polyp visualization and removal.

Primary Analysis -- Stepped Wedge at the Provider Level: We will utilize patient data aggregated to the provider level at monthly intervals to examine how the ADR changes pre- and post-intervention. A provider's monthly ADR is the ratio of the total number of the provider's positive ADR screening results to the total number of patients that the provider screened during the month. Prospective data collection will begin Jan 1st, 2020 and conclude Jun 30, 2022, a 30-month data collection period. Baseline data from 2019 will be included in our analysis to augment the pre-intervention time frame, to enable our intervention to start immediately. ADR

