rates for 2018 will be used to determine randomization strata (high vs. low ADR). Our stepped wedge design yields varying pre- and post-intervention periods for each enrollment wave or “cluster” (Figure 5).

New sites will be enrolled quarterly in 6 waves (12-13 wave, 73 total). For each wave, we will discard the data from the 3-month period where the intervention is being implemented. We will augment baseline data capture by 12 months and we will extend data capture following our final wave by another 12 months to improve estimation of pre/post intervention effects within individual providers who are members of the first and final waves. Under this design, both the pre- and post-intervention data available will range from 12-27 months depending on the wave, with an average of 19.5 months of data.

Clusters	Jan 2019	Jan 2020	Apr 2020	Jul 2020	Oct 2020	Jan 2021	Apr 2021	Jul 2021	Jun 2022
	Baseline 1yr	Step 1	Step 2	Step 3	Step 4	Step 5	Step 6		Follow-up 1yr
1	○	X	○	○	○	○	○	○	○
2	○	○	X	○	○	○	○	○	○
3	○	○	○	X	○	○	○	○	○
4	○	○	○	○	X	○	○	○	○
5	○	○	○	○	○	X	○	○	○
6	○	○	○	○	○	○	X	○	○

X –VA-EQuIP Intervention ○ – Measurement Collected

Figure 5: Enrollment Strategy for Stepped Wedge Trial Design

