We will construct a mixed effects generalized linear model that will act on data aggregated monthly within each provider to estimate the average intervention effect across providers. We will use a Poisson outcome model with a log link to characterize each provider’s monthly rate, where the number of positive screens will be the outcome and the log of the number of total screens will be included as an offset term.^{53,54} In the case of over-dispersion, we will use a negative binomial outcome model. The main predictor of interest will be a pre/post indicator for whether the report card intervention was in effect at a particular month (Intervention). We will additionally control for time since the study began in quarters (Time, coded as a categorical variable) to account for secular trends; as well as site level characteristics obtained from administrative and the quantitative survey data (Aim 1) (urban/rural, cumulative annual procedure volume in 2018 and current volume, site annual ADRs in 2018, use of split dose bowel preparation protocols (SDBP) in 2018, and whether or not ADR was measured in 2018), provider level characteristics (baseline years in practice, primary practice type {academic, hospital employed, private practice}, and baseline annual procedure volume), and baseline patient characteristics aggregated to the provider level (age, sex, race/ethnicity). Since study time will be coded in quarters, it will incorporate seasonal effects in addition to secular trends over the study period. Random effects will be included for both provider and site, where provider is nested within site. Let $PositiveScreens_{ijt}$ denote the observed number of positive screens for the j th provider at site i during month t , and let $TotalScreens_{ijt}$ denote the total number of patients screened. Because the monthly screening rates are expected to be relatively low (≤ 0.30), we assume that the observed number of positive screens, $PositiveScreens_{ijt}$ follows a Poisson distribution with conditional mean λ_{ijt} . We anticipate the following model for λ_{ijt} on a log scale, where $TotalScreens_{ijt}$ is included as an offset term on the right hand side of the equation: $\text{Log}(\lambda_{ijt}) = \beta_0 + \beta_1 Intervention_{ijt} + \beta_2 Time_{ijt} + \beta_3 Urban_i + \beta_4 SiteVolume_i + \beta_5 YrsPractice_{ij} + \beta_6 PracticeType_{ij} + \beta_7 ProviderVolume_{ij} + \beta_8 Age_{ij} + \beta_9 Sex_{ij} + \beta_{10} Race_{ij} + \beta_{11} Volume2018_i + \beta_{12} ADR2018_i + \beta_{13} SDBP2018_i + \beta_{14} ADRMeasured_i + \alpha_i + \mu_{j(i)}$, where β_0 is the intercept, β_2 is a vector of coefficients for the study quarter as expressed by $Time_{ijt}$, α_i indicates the random effect for site i , $\mu_{j(i)}$ indicates the random effect for provider j within site i . $Volume2018_i$ (high/low), $ADR2018_i$ (high/low) and $ADRMasured_i$ (yes/no) are the indicator variables used in stratifying the baseline randomization of sites to waves. We will also examine whether the intervention effect varies by time since intervention and by provider characteristics by considering these interaction terms in the model. Under the proposed Poisson model and logarithmic link function, exponentiating the results will allow us to report rate ratios (RRs), their 95% confidence intervals (CIs), and p-values from the models. Under the generalized linear mixed model the estimated treatment effect, obtained by exponentiating the estimate of β_1 , represents the ratio of the screening rate after versus before implementing the intervention for a given provider.

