
We will plot monthly ADRs for a random sample of endoscopists to examine how the ADR rate changes over time, and to check for the presence of a lagged intervention effect. We expect to see about a one month lag in the intervention effect and plan to drop the outcome data for this period to avoid biased estimates.⁵⁵ We will

examine correlation between successive monthly ADR rates within providers using residual plots and the Durbin-Watson or Durbin's alternative test and include study time lags as appropriate.⁵⁶ If these analyses suggest that the residual covariance deviates substantially from those assumed by the nested random effects model, we will substitute a generalized estimating equation (GEE) analysis under the assumption that outcomes are independent between sites, and use robust standard errors for statistical inference.⁵⁷ The GEE approach can also be used as a fallback if the nested random effect structure of the generalized linear mixed model turns out to be numerically intractable. [As a secondary question we will assess the impact of compliance with the intervention on ADR rate among the providers from Aim 2 who responded to our survey. Compliance will be measured in Aim 1 by dashboard access and participation in one or more collaborative learning sessions. Compliance will be modeled as an interaction with intervention in the model described above, to see if the efficacy of the intervention varies by compliance status.]

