Power Calculation: Our power calculation for the intervention effect comes from a stepped wedge model. Based on 2017 data there were 73 sites with 657 providers performing 155,926 cases per year in our sampling frame. We estimate a 5% loss of site data due to data quality issues. We also estimate a provider attrition rate of 8% from four years of data provided by the national GI program office where attrition rates ranged from 6.9-12%.¹⁵ After accounting for data loss and provider attrition, we expect 69 sites with 571 providers seeing 135,517 patients/year, corresponding to 95 providers/wave and 59 patients/provider/quarter. Note that the number of patients seen by providers factors into our power calculation as it affects the standard errors of the intervention effect, where seeing more patients yields greater power. Our primary outcome is ADR, which we will conservatively estimate as having a range of 13-79% based on prior research^{7,8} and our preliminary data. For cluster randomized trials using implementation designs such as ours, the intra-cluster correlation coefficient (ICC) estimates for patient outcomes are approximately 0.030.⁵⁸ Based on an ADR of 27.5% in the pre-intervention period, we would have about 93% power to detect a 1.0% absolute increase in ADR. This difference is clinically important, because a 1% increase in ADR is associated with a 3.0% decrease in risk of incident CRC, and a 5% decrease in risk of fatal interval CRC.⁷ Power calculations were conducted in R using the swCRTdesign package, and are conservative due to exclusion of three quarters of baseline data, and because the second level of clustering by provider is not considered.^{59,60}

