The second stage analysis will consist of random effects meta-regression to aggregate the provider intervention effects estimated from the first stage.^{61,62} This model will enable us to estimate the average intervention effect across providers accounting for heterogeneity at both the site and provider level by including random effects for both. We include a random effect for provider because although we have included the majority of the eligible providers in the VA system, we conservatively consider the providers included in our analysis to be a random sample from the full possible set of providers.⁶⁴ Konstantopoulos et al. describe a similar multilevel meta-regression analysis where studies are nested within school districts – here we have providers nested within sites.⁶⁵ Our meta-regression model will adjust for the variables used in the randomization stratification procedure (*Volume2018*, *ADR2018*, and *ADRMeasured*), provider-level variables (baseline years in practice and baseline annual procedure volume), and site level characteristics including [split dose bowel preparation protocols (SDBP) in 2018,] urban/rural and cumulative annual procedure volume.

Power Calculation: Our power calculation for the overall intervention effect is estimated from an ITS model after accounting for 5% data loss at the site level and 8% provider attrition. On average a provider has 19.5 months of data in both the pre-intervention and post-intervention periods. Thus we estimate 386 patients/provider or 220,215 patients seen in each period. Again, the number of patients is included in the power calculation because the number of patients seen by providers greatly affects the power of our design. To estimate power, we simulated ITS data with varying intervention effect sizes adapting code provided by Rozario et al.⁶⁶ Under an ITS model with an autocorrelated error structure, we expect to achieve 96.8% power to detect a 1.25% increase in ADR from a pre-intervention rate of 27.5% (based on 1000 simulations). Power calculations were conducted in SAS v 9.0.

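### The stated 93% power does not reflect the discarded implementation quarter; on the planned calendar layout the same calculation gives about 84%

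*Combined protocol and SAP*

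**What the plan says.** The Power Calculation paragraph under Aim 1's primary analysis expects 69 sites and 571 providers after losses, seeing 135,517 patients a year (95 providers per wave, 59 patients per provider per quarter). With an ICC of 0.030 and a pre-intervention ADR of 27.5%, it concludes that "we would have about 93% power to detect a 1.0% absolute increase in ADR". It calls this conservative for two reasons: three of the four baseline quarters were left out, and clustering by provider was ignored. It gives no alpha and does not mention the implementation quarter.

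The design text around Figure 5 says: "For each wave, we will discard the data from the 3-month period where the intervention is being implemented". The figure's legend, "X –VA-EQuIP Intervention ○ – Measurement Collected", separates the implementation cell from the measured cells, and that cell falls in a different calendar column for each wave. The text adds that "both the pre- and post-intervention data available will range from 12-27 months depending on the wave". The start of the primary analysis section says "Baseline data from 2019 will be included in our analysis". The primary model will "control for time since the study began in quarters (Time, coded as a categorical variable) to account for secular trends".

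**The concern.** In a stepped wedge analysis adjusted for calendar quarter, much of the information on the intervention comes from comparing waves that have just crossed over with waves that have not. Removing each wave's crossover quarter removes some of the most informative cells, so the loss of power can far exceed the share of data lost. If the power calculation did not carry that gap in calendar time, its 93% describes a dataset that the plan will not analyse. Calling the figure conservative would then mislead, and a null result would be judged against a power that the design does not have.

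**Working it through.** **Layout.** January 2019 to June 2022 is 42 months, or 4 + 6 + 4 = 14 quarters. With its implementation quarter removed, wave 1 has 4 quarters before and 9 after (12 and 27 months), and wave 6 has 9 and 4. Each wave keeps 39 of 42 months, which matches the plan's 12–27 months, so the discard is already counted there. The time factor is quarter since study start, so each gap stays at its calendar position.

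**Inputs from the power paragraph.** Rates 27.5% and 28.5% (mean p = 0.28, difference δ = 0.01); ICC 0.030; six waves. With sites as clusters there are 69/6 = 11.5 per wave, with 135,517/(69 × 4) = 491 patients per site-quarter. With providers as clusters there are 95 per wave, with 59 patients each per quarter. Alpha is not stated; two-sided 5% is assumed, in line with the planned 95% confidence intervals.

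**Model.** Generalised least squares on cluster-quarter proportions, with a fixed effect for each quarter, one intervention indicator and a random cluster intercept:

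- σ² = p(1 − p) = 0.28 × 0.72 = 0.2016
- τ² = ICC × σ²/(1 − ICC) = 0.03 × 0.2016/0.97 = 0.00624
- covariance within a cluster: V = (σ²/n)I + τ²J, where J is the all-ones matrix
- SE(δ) = square root of the intervention element of [Σ X′V⁻¹X]⁻¹, summed over clusters, with discarded cells omitted from X and V
- power = Φ(δ/SE − 1.96)

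| Layout | SE, sites (points) | Power, sites | Power, providers |
|---|---|---|---|
| Implementation quarter kept, 1 baseline quarter (11 quarters) | 0.290 | 93.2% | 93.4% |
| Quarter removed and time closed up (10 gap-free quarters) | 0.295 | 92.3% | 92.6% |
| Quarter discarded in calendar time, 1 baseline quarter | 0.353 | 80.9% | 81.3% |
| Quarter discarded in calendar time, all 4 baseline quarters (the planned dataset) | 0.338 | 84.2% | 84.2% |

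The first row reproduces the plan's figure: 0.01/0.00290 − 1.96 = 1.49, and Φ(1.49) = 0.93. Coding the kept quarter as control or as intervention makes no difference. In the last row, 0.01/0.00338 − 1.96 = 1.00, and Φ(1.00) = 0.84.

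Rows two and three hold the same ten quarters per cluster, so the 11-point difference between them comes from calendar alignment, not from the amount of data. Restoring the other three baseline quarters recovers about 3 of the roughly 12 points lost between rows one and three.

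**Detectable difference on the planned layout.** At 93% power: (1.96 + 1.476) × 0.338 = 1.16 points. At 80% power: (1.96 + 0.842) × 0.338 = 0.95 points.

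**Sensitivity**

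- With sites as clusters, an ICC from 0.01 to 0.10 moves no figure by more than 0.3 points.
- One-sided 5% gives 96.5%, 95.9%, 88.3% and 90.6% for the four rows.
- Simulation (1,500 binomial datasets per layout; Poisson log-link model with offset, fixed site and quarter effects, dispersion-scaled standard errors) gives 93.6%, 92.5%, 82.8% and 83.8%, with Monte Carlo error of about 1 point.
- Unscaled Poisson standard errors in the same simulation give 87.0%, 85.9%, 72.7% and 73.2%. All layouts fall, and the ordering holds.
- Adding a provider variance component on the planned layout gives 85.9%, 87.0% and 88.7% if providers account for 2%, 5% and 10% of total variance. These shares are assumed; the documents give none.
- The analysis text also says: "We expect to see about a one month lag in the intervention effect and plan to drop the outcome data for this period". If that month lies outside the discarded quarter, power is about 80%. The text does not settle this, and the conclusion does not rest on it.

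**The case against.** Four points can be made for the plan.

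- **The 81% figure also belongs to a dataset that will not be analysed**, since all of 2019 will be used. That is right. It is only the like-for-like comparison with the power section's own baseline exclusion; about 84% is the figure for the planned data.
- **Provider clustering is a real conservative factor of unknown size**, so the discard cannot be called larger with certainty. This stands in part. At the assumed 2–10% of variance, the shortfall against 93% narrows to about 4–7 points, and at 87% power the miss probability is 13% rather than 16%. Providers would need to account for about 23–25% of total variance to return to 93%, and nothing in the documents supports that.
- **The replacement figures depend on the model.** They move with the standard error used, the provider variance and alpha, and the package call is not shown. This is why 84% and 1.16 points are indicative only, and why the layout actually run cannot be identified.
- **The consequence is modest.** The sample is the set of eligible sites, so it would not change, and results will be reported as rate ratios with confidence intervals. This is accepted; it makes the point one of reporting and interpretation.

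The interrupted time-series power section, which says "On average a provider has 19.5 months of data in both the pre-intervention and post-intervention periods", concerns a different calculation. It shows only that the three months are netted out of the average there.

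**Conclusion.** The concern holds. The 93% is reproduced, or nearly so, only on layouts that the plan rules out. On the calendar layout it describes, the same type of calculation gives about 84% for a 1.0-point increase. The miss probability is then about 16%, roughly twice the stated 7%, and 93% power corresponds to about 1.16 points. This rests on a two-sided 5% test, the stated ICC, a single cluster level and a linear approximation to the planned Poisson mixed model, which may differ in either direction. Both of the plan's reasons for calling the figure conservative point the right way. The first is too small to offset the discarded quarter, the second cannot be sized from the documents, and the opposing factor is not mentioned. Under the two-sided linear calculation the planned layout stays above 80%, so the design is not in question. The stated figure should be corrected.

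**What to change.** Rerun the stepped wedge power calculation on the actual layout: 14 calendar quarters, with each wave's implementation quarter missing. In the Power Calculation paragraph:

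- state alpha and sidedness, and the layout used;
- say whether the one-month lag lies inside the discarded quarter;
- replace the 93% with the recomputed power for 1.0 point, or keep 93% and give the difference it applies to (indicatively about 84%, or about 1.16 points);
- keep the two existing remarks as statements of direction only, add the discarded quarter beside them as a factor that lowers power, and stop describing 93% as conservative.

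The cost is one rerun and a few sentences. The stated power becomes less favourable; sites, waves and analysis stay as they are.

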Secondary Analysis -- Interrupted Time-Series (ITS) at the Provider Level: While the analysis described above will be considered primary, our stepped wedge design coupled with our focus on provider performance provides opportunity for several analysis options. As a secondary analysis, we will estimate the average intervention effect across providers using a two-stage approach. In the first stage, we will implement ITS models within each provider, estimating the intervention effect for each provider. In the second stage, we will use a meta-regression approach to combine results across providers to estimate the mean and the standard deviation (on the log scale) of the intervention effect across providers.^{61,62} This analysis is conventional for pre/post analysis of interventions implemented at different time points for different units,^{62,63} and has the advantage of evaluating both the overall intervention effect and the heterogeneity in the treatment effect across sites and providers. However, it focuses on pre/post comparisons within providers and does not allow for comparisons between treatment and control at the same time points as is done in our stepped wedge analysis.

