The first stage ITS analysis will consist of segmented regression with an autoregressive error model to account for the correlation between successive monthly ADRs. As described in the primary analysis, we will plot monthly ADRs for a random sample of endoscopists to guide our ITS modelling strategy. We will also use these plots to assess whether to include seasonal effects, which would be included as a categorical quarter variable in the model. We assume that a provider's observed number of positive screens during month t , $PositiveScreens_t$, follows a Poisson distribution with conditional mean λ_t . Our basic ITS model for λ_t for a particular provider has the following form: $\text{Log}(PositiveScreens_t) = \beta_0 + \log(TotalScreens_t) + \beta_1 Intervention_t + \beta_2 Time_t + \beta_3 Time\text{-}After\text{-}Intervention_t + \beta_4 Age + \beta_5 Sex + \beta_6 Race + \beta_7 Season_t$, where t indicates time coded in months.⁵⁵ In this ITS analysis, time is coded monthly and treated as a continuous variable instead of coding it as a categorical variable as in the stepped wedge analysis. The main predictors of interest will include the immediate intervention effect (*Intervention*) and whether the monthly post-intervention time trend differs from the pre-intervention time trend (*Time-After-Intervention*). Autocorrelation will be examined using residual plots and the Durbin-Watson or Durbin's alternative test and corrected using lagged study time variables as appropriate.⁵⁶ Each model will provide a RR estimate, 95% CI and p-value for a provider's intervention effect.

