Explanatory Analysis – Stepped Wedge and ITS analyses at the Patient Level: One potential limitation of the analyses described above is that we are aggregating patient-level data to the provider month-level. The analysis of aggregated data is susceptible to Simpson's paradox, where the direction of a relationship between an exposure and outcome can change when the data is analyzed at an aggregated level versus a partitioned level.^{67,68} This is due to insufficient adjustment for confounders when the data is analyzed at the aggregated level. The ITS analysis is particularly vulnerable to Simpson's paradox as there is no comparison of intervention and controls at the same point in time, but rather this analysis focuses on pre/post comparisons within providers. Thus, there is potential for confounding due to case-mix differences in patients seen at different points in time. To overcome this paradox, we will re-examine both our primary stepped wedge analysis and our secondary ITS analysis using data at the patient observation level. The modeling will be very similar, where we will use Poisson outcome models, but there will be no offset term at the patient level. The interpretation of the results will be the same as before. For the stepped wedge analysis, the exponentiated coefficient of intervention will represent the ratio of the screening rate after implementing the intervention versus before, for a given provider. For the ITS analysis, the first stage modeling will yield the ratio of each providers screening rate after implementing the intervention versus before. The second stage will yield a pooled estimate of the intervention RR across providers.

Aim 2: Evaluation of VA-EQuIP implementation

[Evaluation Overview: We will use a mixed-methods approach to perform the evaluation. This multi-faceted evaluation consists of three components: monitoring of VA-EQuIP usage statistics, pre/post surveys of quality stewards and providers, and qualitative interviews with quality stewards and individual providers. The approach will capture key RE-AIM (1a) and COM-B (1b) domains with qualitative assessments to explore barriers and facilitators to implementation and components of provider behavior change.]

Evaluation Measures and Outcomes:

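### In the single-provider ITS equation Age, Sex and Race have no month index, so as written the model does not adjust for them

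*Combined protocol and SAP*

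**What the plan says.** All references are to Aim 1 of the combined protocol and SAP.

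- **Secondary Analysis (ITS), structure.** The analysis has two stages: "In the first stage, we will implement ITS models within each provider, estimating the intervention effect for each provider". A random-effects meta-regression then pools the provider estimates.
- **Secondary Analysis (ITS), equation.** The first-stage model "for a particular provider has the following form": a Poisson segmented regression with a log offset for exams, "where t indicates time coded in months". The last terms are "\beta_4 Age + \beta_5 Sex + \beta_6 Race + \beta_7 Season_t". Season carries the index; Age, Sex and Race do not.
- **Primary Analysis (stepped wedge).** This is the only place where the patient covariates are defined: "baseline patient characteristics aggregated to the provider level (age, sex, race/ethnicity"). In that equation they are indexed by site and provider, again without a month.
- **Secondary Analysis (ITS), second stage.** The adjustment list contains the stratification variables, site characteristics and "provider-level variables (baseline years in practice and baseline annual procedure volume"). Patient age, sex and race are not on it.
- **Explanatory Analysis (patient level).** The plan accepts that in the ITS "there is potential for confounding due to case-mix differences in patients seen at different points in time", and commits that "we will re-examine both our primary stepped wedge analysis and our secondary ITS analysis using data at the patient observation level".

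**The concern.** The three patient covariates look like case-mix adjustment. They can act as such in the primary mixed model, where their values differ between providers. In a regression that contains only one provider, a single baseline value does not vary over the rows, so it carries no information about that provider's months.

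This matters because the ITS compares each provider with himself or herself over time and has no concurrent control. If the patients seen after rollout differ from those seen before, the difference goes into the level or slope change, which are the two quantities the ITS is meant to estimate. A reader of the equation would believe that age, sex and race had been accounted for. Pooling over many providers does not remove a bias that they share.

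**Working it through.** **1. The plan's own ITS figures.** Inputs from the two power sections: 571 providers, 135,517 patients per year, 19.5 months per period, ADR 27.5% rising to 28.75%.

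- Patients per period: 135,517 × 19.5/12 = 220,215. Per provider: 220,215/571 = 385.7 (stated 386). Both reproduce.
- Exams per provider-month: 135,517/571/12 = 19.8.
- Target effect: ln(28.75/27.5) = 0.0445 in log rate ratio.
- Power, taking 19 months before and 20 after, independent Poisson errors and two-sided alpha 0.05 (all assumed). The standard error of the level change is 0.2747 for one provider and 0.2747/√571 = 0.0115 pooled. Power = Φ(0.0445/0.0115 − 1.96) = 97.2%, or 96.8% with quarterly season terms. The plan states 96.8%.
- The plan assumes autocorrelated errors but gives no coefficient. In the same approximation without season terms, AR(1) of 0.1 gives 93.8% and 0.3 gives 81.0%. The match is therefore consistent with the plan but does not confirm it.

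**2. Rank of the one-provider design, 39 monthly rows.**

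| Design | Columns | Rank |
|---|---|---|
| Intercept, Intervention, Time, Time-After-Intervention, 3 season indicators | 7 | 7 |
| The same plus constant Age, Sex, Race | 10 | 7 |
| The same plus Age, Sex, Race varying by month | 10 | 10 |

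A constant column equals a number times the intercept column, so this result does not depend on the data.

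**3. Effect on the fit.** In one simulated provider series, the model without the covariates and the model with constant covariates gave the same Intervention estimate (−0.2259), standard error (0.3076) and deviance (25.00). The redundant terms do no harm, but they also do nothing.

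**4. Does the second stage restore the adjustment?** No. The covariates are not listed there. If they were, baseline values could explain why effects differ between providers, but not a change in patients within a provider.

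**5. What could be at stake (assumed inputs; the documents give none).** If mean age steps up by *d* years at rollout and the detection rate ratio per year of age is *r*, the bias in the level change is about *d* × ln(*r*).

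- Low: 0.5 × ln(1.01) = 0.0050, which is 11% of 0.0445.
- High: 2 × ln(1.02) = 0.0396, which is 89% of 0.0445.
- High case confined to one wave in six, with equal weights: 0.0396/6 = 0.0066, about 15%.

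A simulation of the high case with no true effect used 200 exams per month to reduce noise. The mean Intervention estimate was 0.044 with no covariate, 0.044 with a constant covariate and 0.002 with monthly mean age (Monte Carlo standard errors about 0.004, 0.004 and 0.005).

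**6. Cost of indexing by month.** At about 20 exams per month, with assumed patient distributions, adding the monthly covariates raised the pooled standard error by 5 to 9%. From step 1, 0.0115 × 1.05 = 0.0121 and 0.0115 × 1.09 = 0.0125. The independent-error power moves from 97.2% to about 96% and 94%.

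**The case against.** The strongest reply is that the index was simply left off. The ITS section does not itself call these values baseline. The document's notation is also loose elsewhere: the displayed primary equation omits the offset that the text says it contains, and the ITS equation writes the log of the count where the text defines a conditional mean. The model is described as a basic form. That reading is possible, but it needs the same edit, because the plan nowhere defines a monthly version of the covariates.

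Three further points stand and limit the concern.

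- A reader might infer that the ITS has no case-mix control at all. The documents do not support that. Each provider is his or her own control, so stable differences between providers cancel. The Time term takes up smooth log-linear drift, and Season, where included, takes up seasonal change. Rollout is staggered over six waves, so one calendar shift would not coincide with every provider's start.
- The plan discloses the case-mix weakness of the aggregate ITS and schedules a patient-level re-analysis, in which age, sex and race vary within a provider and can be estimated. That analysis is labelled explanatory and lists no covariates, but it could supply the adjustment.
- Monthly means from about 20 exams are noisy, so the repair has a price, as step 6 shows.

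**Conclusion.** The point holds for the provider-month ITS as written: the stated adjustment for age, sex and race is not delivered, because terms fixed at one value per provider are aliased with the intercept. This rests on reading the covariates by the plan's only definition of them.

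The remaining exposure is a step or slope change in case mix aligned with rollout. Its size cannot be taken from the documents. The 11% to 89% range rests on assumed age shifts and rate ratios and on every provider being affected; it is not an estimate for this trial.

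A reader might go further and conclude that the provider rate ratios are corrupted or that the trial's main result is at risk. Neither follows. The aliased terms leave the intervention estimate and its standard error unchanged. In the primary stepped-wedge model the same covariates vary between providers and can be estimated, and the stated power does not depend on this point. It should be corrected before analysis, as a defect in a secondary analysis.

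**What to change.** In the first-stage ITS equation write `Age_t`, `Sex_t` and `Race_t`, and define them in the text as provider-month summaries: mean age, proportion male and one race/ethnicity proportion among the exams counted in that month's denominator. In the same section, cite the patient-level ITS as the case-mix sensitivity check and list age, sex and race among its covariates.

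This changes one equation and adds two or three sentences. It needs no new data and no change in sample size. The price is three noisy covariates in a series of about 39 points and the modest loss of precision shown in step 6. If that is judged not worth paying, the editorial alternative is to delete the three terms, state that the provider-month ITS is not adjusted for patient age, sex and race, and name the patient-level ITS as the adjusted version.
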